7.9 Handling of Partial Dates for Other Data

Other data with partial dates will be listed as collected. For other calculations of time intervals, the dates will be imputed with the first day of the month (if the day is missing) or with January 1 (if both day and month are missing).

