7.4 Handling of Partial Dates for Adverse Events

If the year of the start date is missing or the start date is completely missing, the first dose date will be used. If the year of the end date is missing or the end date is completely missing, the event will be regarded as ongoing and do not impute. Impute AE end date first if both AE start date and end date are partially missing.

If end date of an adverse event is partially missing, impute as follows:

- If the day of the month is missing, the onset day will be set to the last day of the month.
- If the onset day and month are both missing, the day and month will be assumed to be December 31.
- If the imputed end date > death date, then set to death date.

If start date of an adverse event is partially missing, impute as follows:

- If the day of the month is missing, the onset day will be set to the first day of the month unless it is on or after the same month and year as study treatment. In this case, the onset date will be assumed to be the first dose date of treatment.
- If the onset day and month are both missing, the day and month will be assumed to be January 1 when the year is on or after the year of study treatment. If the year is prior to year of first dose, December 31st will be used. The event onset will be coded to the first dose date of treatment if year is the same as the year of first dose date to conservatively report the event as treatment-emergent.
- If the imputed AE start date is after the AE end date (maybe imputed), then update the AE start date with the AE end date as the final imputed AE start date.
- If the imputed start date > death date, then set to death date
- If the imputed end date is before imputed start date, the AE event will be treated as treatment emergent AE and report it as data issue.

Imputation of partial dates is used only to determine whether an event is treatment-emergent; data listings will present the partial date as recorded in the eCRF.

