7.8 Handling of Missing/Partial dates for Post-study Anticancer Therapy/Radiotherapy

For records with completely missing start date, end of treatment date will be used as the start date of post-study therapy/radiotherapy. If the start date of post-study anticancer therapy/radiotherapy is partially missing, impute as follows:

- If the day of the month is missing, the start day will be set to the last day of the month unless it is on the same month and year as last dose of the study treatment. In this case, the start date will be assumed to be the last dose date + 1.
- If the day and month are both missing, the start date will be set to January 1st unless it tis on the same year as the last dose date of the study treatment. In this case, the start date will be assumed to be the last dose date + 1.
- If only month is missing, year and day are present, set the missing month to the month of the last dosing date of the study drug unless the day is prior to the last dose day. In this case, impute the missing month as the month of last dose date + 1

No imputation is needed for post-study therapy/radiotherapy end date.

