7.10 Handling of Missing Data

Missing data will not be imputed, except for:

- missing date parts, i.e., partial dates, discussed above.
- missing efficacy assessments discussed in Section 9.
- missing AEs relationship to study drug, discussed in Section 12.2.

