8.9.1 Duration of Treatment

Duration of treatment will be calculated as:

Duration of treatment (weeks) = (min (last dose date of study drug, death date, data cutoff date) - first dose of study drug +1)/7

For participants who have discontinued study treatment, the last dose date will be used as the treatment end date. For participants with ongoing treatment at the time of data extraction, the data cutoff date will be used.

If a participant has a recorded date of death that precedes both the last dose date and the data cutoff date, the death date will be used as the treatment end date.

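### A partial death date is back-dated with no floor (SAP 7.9) and can then make treatment duration too short or negative (SAP 8.9.1)

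*SAP*

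**What the plan says.** SAP 7.4 to 7.8 give partial-date rules for adverse events, medications and procedures, screening dates, prior anticancer therapy and post-study therapy. None of them imputes a death date. Sections 7.4 and 7.5 use it only as a cap on other dates, for example "If the imputed start date > death date, then set to death date".

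SAP 7.9 covers all other data. Such dates are listed as collected, but for intervals the rule is "For other calculations of time intervals, the dates will be imputed with the first day of the month (if the day is missing". When the month is unknown as well, the date becomes 1 January of the known year. No lower bound and no data-issue check are attached. SAP 7.10 then confines date imputation to "missing date parts, i.e., partial dates, discussed above".

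SAP 8.9.1 computes duration of treatment in weeks as "min (last dose date of study drug, death date, data cutoff date) - first dose of study drug +1)/7". Its prose adds a condition, "If a participant has a recorded date of death that precedes both the last dose date and the data cutoff date", and in that case "the death date will be used as the treatment end date".

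SAP 7.8 treats a similar problem differently. When a partial start date for post-study therapy shares the month (or the year, if the month is missing too) with the last dose, "In this case, the start date will be assumed to be the last dose date + 1".

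**The concern.** A death cannot precede a dose that was taken. Yet a partial death date goes by default to the earliest day of the known month or year, and nothing holds it at or after the last dose. Because the SAP 8.9.1 formula takes a minimum that includes death, an imputed date can displace a last dose date that is known exactly. With complete and correct dates the death term in that minimum never acts, so it bites only on wrong or imputed dates.

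What is at stake is the exposure summary. Duration of treatment is tabulated by dose level and schedule (SAP 8.9), and cohorts after Dose Level S may be as small as 3 (SAP 4.1). Actual dose intensity (SAP 8.9.4) divides cumulative dose by duration of exposure, and relative dose intensity (SAP 8.9.5) divides that by the planned intensity. If the SAP means the same duration there, the error carries through to both.

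**Working it through.** The documents give no figure for this point, so there is none to reproduce. The check applies the plan's formula to illustrative dates, which are assumptions.

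**Inputs.** Imputation rule: SAP 7.9. Duration: SAP 8.9.1, weeks = (min(last dose, death, cutoff) - first dose + 1)/7. Dose intensity: SAP 8.9.4, cumulative dose / (duration in days / cycle length). The data cutoff is taken to be later than all the dates used.

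**Main example.** First dose 10 March 2025, last dose 20 June 2025.

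| Death date as recorded | Imputed by 7.9 | Treatment end by 8.9.1 | Days | Weeks |
|---|---|---|---|---|
| Complete, on or after 20 June | none needed | 20 June | 103 | 103/7 = 14.7 |
| June 2025 | 1 June 2025 | 1 June | 84 | 84/7 = 12.0 |
| 2025 | 1 January 2025 | 1 January | -67 | -67/7 = -9.6 |

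**When it happens.** The last dose must fall after the imputed date, in the same month as the death (day missing) or the same year (day and month missing). A last dose in an earlier month is untouched when only the day is missing. With first dose 6 January, last dose 20 February and death in March 2025, the result is 6.57 weeks with or without a floor.

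**Range of shortening.** The loss is last dose minus imputed death date.
- Day missing: 0 to 30 days, or 0 to 30/7 = 4.3 weeks.
- Day and month missing: 0 to 364 days, or 0 to 364/7 = 52 weeks (365 days in a leap year).

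**When it turns negative with only the day missing.** If first dose is on day f of the death month, the end date is day 1 and duration is (1 - f + 1)/7 = (2 - f)/7 weeks. That is 0 at f = 2, negative from f = 3, and -4.14 at f = 31. With first dose 10 March and last dose 20 March 2025, death in March 2025 gives (2 - 10)/7 = -1.14 weeks instead of 11/7 = 1.57.

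**Dose intensity.** If duration of exposure equals the SAP 8.9.1 duration, cumulative dose and cycle length are unchanged and the ratio of wrong to right is the inverse ratio of durations.
- June 2025: 103/84 = 1.23, about 23% too high.
- 2025: 103/(-67) = -1.54, a negative intensity.

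**Effect on a small cell.** In a cell of 3 participants, one such case lowers mean duration by (103 - 84)/7/3 = 0.9 weeks, or by (103 + 67)/7/3 = 8.1 weeks in the year-only case.

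**With a floor at the last dose.** The minimum returns 20 June in both partial cases, and duration is 14.7 weeks.

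**The case against.** The strongest reply is that the prose of SAP 8.9.1 speaks of a recorded date of death. On that reading the clause guards against a dose logged after a known death, and an imputed date would not trigger it. The same section also makes the last dose date the treatment end for those who have discontinued. This is a fair reading of the prose. But the formula carries no such limit, and a programmer working from it would use whatever death date is in the dataset. The conflict between formula and prose stands and needs resolving.

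SAP 7.9 does not name death either. It applies because nothing else visible does, and SAP 7.10 allows no imputation outside the listed rules except in the areas it names.

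The reply on frequency largely stands. Telephone survival contacts, about every 90 days after discontinuation, make partial death dates plausible. But many such deaths will fall in a later month than the last dose and do no harm when only the day is missing. The year-only case needs a death whose month stays unknown despite those contacts. A negative duration would also be noticed on review; a merely shortened one might not.

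A reader might infer more than the documents support:
- **Treatment-emergent adverse event counts.** SAP 7.4 caps imputed adverse event dates at the death date, so a back-dated death might seem to push events before first dose. But SAP 7.9 imputes only for time intervals, and nothing visible feeds its result into 7.4.
- **Survival or progression endpoints.** The efficacy section is not in the released text and may have its own death-date rule.
- **Lower dose intensity.** Duration is in the denominator, so a shorter positive duration raises it.

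**Conclusion.** The gap is real and confined to exposure. On the visible text, a partial death date used in an interval is set to the earliest day of the known period, and the SAP 8.9.1 formula lets it override a known last dose. In the example, 14.7 weeks becomes 12.0 or -9.6. Dose intensity is inflated by about 23% or turns negative, provided duration of exposure means the SAP 8.9.1 duration.

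The conclusion assumes that SAP 7.9 governs death dates by default, that the formula is programmed as written, and that the last dose falls after the imputed date within the same month or year. The documents do not say how many death dates will be partial; the number of participants affected is probably small. The size of the shift in the death date should not be read as the loss of treatment time, which is only last dose minus imputed death and is often zero. No conclusion is drawn on adverse event counts or time-to-event endpoints. The exposure tables are descriptive, but the rule as written can give impossible values and should be corrected before programming.

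**What to change.** Make two changes to the SAP.

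1. In 7.9, add a rule for death dates. Impute a partial death date to the later of (a) the first day of the known month, or 1 January if only the year is known, and (b) the last date known alive, which is never earlier than the last dose date. Cap the result at the end of the recorded month or year and at the data cutoff. Report any conflict, such as a dose logged after the recorded month of death, as a data issue, as 7.5 already does for medications. The cap is needed because a floor set one day after last contact could leave the recorded month: last contact on 30 June with death in June would give 1 July.
2. In 8.9.1, state that only a complete recorded death date, not an imputed one, may end treatment before the last dose date, and make the formula match. State also whether duration of exposure in 8.9.4 is this same duration.

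The cost is a few sentences and one derived last-known-alive date, built from doses, visits, laboratory samples and contacts already collected. No new data are needed.

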7.10 Handling of Missing Data

Missing data will not be imputed, except for:

- missing date parts, i.e., partial dates, discussed above.
- missing efficacy assessments discussed in Section 9.
- missing AEs relationship to study drug, discussed in Section 12.2.

8. STUDY SUBJECTS

8.1 Subject Enrollment

The number of subjects in each analysis set will be summarized for all patients. Analysis set flag for each subject will be listed together with the dose level and dose schedule for all patients.

8.2 Subjects Disposition

Subjects disposition will be summarized by, dose level and dose schedule, and overall for the Safety Population including:

- Number of subjects in each analysis population
- Number of subjects treated.
- Number of subjects who discontinued RP-1664 and primary reasons of discontinuation.
- Number of subjects who completed the study as per protocol.
- Number of subjects who discontinued study and primary reasons of discontinuation.

The primary reason for treatment discontinuation and study discontinuation will be summarized by categories in eCRF. Subjects' disposition will be listed for the Safety Population.

8.3 Protocol Deviations

Major protocol deviations are protocol deviations that might significantly affect the completeness, accuracy, and/or reliability of the study data or that might significantly affect a patient's rights, safety, or well-being. Protocol deviations will be identified and classified prior to any database snapshot or database lock. Only major and critical protocol deviations will be summarized in a CSR for the Safety Population.

8.4 Demographics and Other Baseline Disease Characteristics

Demographic, baseline characteristics and baseline disease characteristics will be tabulated using descriptive statistics for the Safety Population. The following variables will be included:

- Age at Consent (years)
- Sex at birth
- Race
- Ethnicity
- Height (cm)
- Weight (kg)
- BMI (body mass index, kg/m²), defined as weight (kg) / height (m)²
- ECOG at Screening
- Lansky Performance Status

- Time from initial diagnosis to first dose (Months) and time from diagnosis at Screening to first dose (months), calculate as (Date of Informed Consent Date of diagnosis + 1)/30.4375
- Tumor types
- Genotypes (TRIM37, Genomically unaltered TP53, RAD51C, PPM1D, BRIP1, RNF43, Chromosome region 17q23, Others)
- Histological Categories (Andenocarcinoma, Squuamous Cell, and other)
- Histology Subtypes (Adrenal and other neuroendocrine histology, central nervous system histology, breast histology, etc.)
- Grade at disease diagnosis (Gx, G1, G2, G3, G4, Unknown, Other)
- Time from first presentation of locally advance disease to enrollment (months), calculate as (Date of Informed Consent Date of diagnosis + 1)/30.4375
- Time from diagnosis of disease to metastasis (months), calculated as (Date of diagnosis for metastatic disease Date of diagnosis + 1)/30.4375

Conversions for height and weight are as follows:

```
Height (cm) = Height (inches) \times 2.54
```

Weight (kg) = Weight (lb) $\times 0.4536$

Demographics and baseline disease characteristics will be tabulated and listed in the Safety Population.

8.5 Prior Anti-Cancer Systemic Therapy

Prior Anti-cancer systemic therapy will be summarized, including

- Prior systemic therapy (Yes, No)
- Number of lines of prior systemic therapy
- Time from the most recent prior systemic therapy to the first dose of the study drug (months), calculated as: (Date of first dose of study drug End date of most recent prior systematic therapy +1)/30.4375
- Best overall response (BOR) from last prior systemic therapy
- Reason for therapy ended from last prior systemic therapy (Completion of therapy as planned, Progressive Disease, Toxicity, Other)

Prior anti-cancer systemic therapy will be summarized and listed for Safety Population.

8.6 Prior Anti-Cancer Radiotherapy

Prior Anti-cancer radiotherapy will be summarized, including

- Prior radiation therapy (Yes, No)
- Radiotherapy Site

- Reason for Administration
- Time from most recent radiotherapy to first dose of the study drug (months), calculated as: (Date of first dose of study drug End date of most recent prior radiotherapy+1)/30.4375

Prior anti-cancer radiotherapy will be summarized and listed for Safety Population.

8.7 Medical History

Medical history will be coded using the latest Medical Dictionary for Regulatory Activities (MedDRA) version available.

The frequency count and percentage of subjects experiencing any medical conditions will be tabulated by System Organ Classifications (SOC) and Preferred Term (PT). If a PT or SOC was reported more than once for a subject, the subject would only be counted once in the incidence for that preferred term or system organ class.

Medical history data will be summarized and listed for the Safety Population.

8.8 Prior and Concomitant Medications and Procedures

Prior and concomitant medications and procedures will be coded using the latest World Health Organization Drug (WHODrug) Dictionary version available. Unless specified otherwise, summaries of prior and concomitant medications will be presented by Anatomical Therapeutic Class (ATC) Level 2 and PT with numbers and percentages for subjects in the Safety Population.

A subject who takes more than one medication will be counted only once if these medications belong to the same ATC Level 2 classification.

In the summary tables, prior medications and concomitant medications and procedures will be presented by decreasing frequency of subjects overall within each ATC Level 2 class and then similarly by decreasing frequency of subjects overall within each preferred term. In cases of ATC Level 2 classes or preferred terms with equal frequencies, medications will be sorted alphabetically.

Prior medications/procedures are defined as those medications/procedures that started prior to the first administration of the study drug. Concomitant medications/procedures are defined as those medications/procedures taken on or after the first administration of the study drug till 30 days after the last dose of study treatment, or the start of subsequent anticancer therapy, whichever occurs first.

A prior medication/procedure could also be classified as "both prior and concomitant medication/procedure" if the end date is on or after first dose of study treatment. In the listing, it will be indicated whether a medication is prior-only, concomitant-only, or both prior and concomitant medication.

8.9 Study Drug Exposure and Compliance

RP-1664 exposure will be summarized and grouped by dose level and dose schedule, and overall for overall treatment period and treatment cycles for the Safety Population by the following parameters:

- Duration of treatment (week)
- Number of cycles treated

- Number and percentage of patients treated for 1-2 Cycles, 3-4 Cycles, 5-6 Cycles, 7-8 Cycles, 9-10 Cycles, 11-20 Cycles, >20 Cycles
- Any dose interrupted
- Any dose increases from the initial assigned dose
- Actual cumulative dose
- Actual and Relative dose intensity.

The PK lead-in period (Cycle 0) will not be considered as part of the treatment exposure window for the purpose of exposure analysis.

8.9.1 Duration of Treatment

Duration of treatment will be calculated as:

Duration of treatment (weeks) = (min (last dose date of study drug, death date, data cutoff date) - first dose of study drug +1)/7

For participants who have discontinued study treatment, the last dose date will be used as the treatment end date. For participants with ongoing treatment at the time of data extraction, the data cutoff date will be used.

If a participant has a recorded date of death that precedes both the last dose date and the data cutoff date, the death date will be used as the treatment end date.

8.9.2 Dose Reduction

Dose reduction is defined as 1) decreased in the total daily dose level or, 2) a decrease in the number of consecutive day (e.g., from 2 weeks on/1 week off to 3 days on/4 days off) or weeks (e.g. 2 weeks on/1 week off to 2 weeks on/2 weeks off).

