At Dose Level S, the cohorts will be expanded to a minimum of 3 participants to further evaluate safety, PK, and pharmacological activity. Evidence of pharmacologic activity can include Grade ≥ 2 drug-related toxicity at any cycle, PK data demonstrating exposure levels predicted to be efficacious based on nonclinical studies, or other evidence of treatment-related activity as agreed on by the SRC. Dose decisions will be based on assessments in 2 or more dose-limiting toxicity (DLT) evaluable participants completing the DLT evaluation period. Any escalation of RP-1664 after Dose Level S will be in increments up to 75% as agreed upon by the SRC and will enroll cohort sizes of N \geq 3.

RP-1664 Escalation

	Escalation Plan	
Dose Level	Daily (mg) or % of previous dose increment	
1	10 mg	
2	Up to 30 mg	
3 to S	Up to 100% increases until Dose Level S	
S	Expand cohort at same dose	
S1 to MTD or tolerated and pharmacologically active dose	Up to 75% increases until MTD or tolerated and pharmacologically active dose	

Additional treatment schedules, including daily dosing, 3 days on/4 days off, 1 week on/1 week off, or 2 weeks on/2 weeks off may also be explored to mitigate AEs and/or improve efficacy. If an additional schedule is tested, the starting dose of RP-1664 may be as high as the highest total daily dose that cleared DLT evaluation. The decision to test one or more of these schedules and set the starting dose level will be agreed upon by the SRC, and will take into consideration all available safety, efficacy, pharmacodynamic, and PK data.

Dose modifications, including adjustments to treatment frequency (e.g., QD to BID or BID to QD dosing), schedule changes, or intra-participant dose escalations, will be allowed for participants to manage AEs and/or maximize RP-1664 exposure and clinical benefit. These changes in doses or schedules will be allowed only to previously SRC-approved levels or frequencies that have been cleared for DLT evaluation.

The food effect portion of the trial will be conducted at selected centers and may start at Dose Level 3 or once Dose Level S is reached. The fasting recommendation for RP-1664 in the general trial population may be revised to allow dosing with food after the PK profiles of 12 evaluable participants have been analyzed.

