S	Expand cohort at same dose
S1 to MTD or tolerated and	Up to 75% increases until MTD or tolerated
pharmacologically active dose	and pharmacologically active dose

Evaluation of the PK data after at least 6 participants, with sufficient data to derive PK parameters, may trigger adjustment of the daily dosing frequency of RP-1664 to allow for twice-daily (BID) dosing. BID dosing may be initiated based on observed participant outcomes and PK parameters such as, but not limited to, t1/2 is < 12 hours or the C_{max} : C_{min} ratio is > 10. Any decision to move from QD to BID dosing during the trial will be made after consultation with the SRC. If BID dosing is initiated, the Sponsor in agreement with SRC, can elect to continue or cease enrollment in QD dosing cohorts based on available data.

Additional treatment schedules, including daily dosing, 3 days on/4 days off, 1 week on/1 week off, or 2 weeks on/2 weeks off may also be explored to mitigate AEs and/or improve efficacy. If an additional schedule is tested, the starting dose of RP-1664 may be as high as the highest total daily dose that cleared DLT evaluation. The decision to test one or more of these schedules and set the starting dose level will be agreed upon by the SRC and will take into consideration all available safety, efficacy, pharmacodynamic, and PK data.

The food effect portion of the trial will be conducted at selected centers and may start at Dose Level 3 or once Dose Level S is reached. The fasting recommendation for RP-1664 in the general trial population may be revised to allow dosing with food after at least 4 participants have been evaluated in the food effect portion of the trial.

Expansion cohorts may be opened if at least one safe dose and schedule at which clinical activity is identified and agreed upon by the SRC. Up to 20 efficacy evaluable participants in each expansion cohort can be enrolled to further evaluate the safety, PK, pharmacodynamic, and preliminary efficacy of RP-1664 at the selected dose level(s). Enrollment in expansion cohorts may be limited to specific tumor types and/or genomic profiles based on assessment of clinical activity by the Sponsor in the dose escalation portion and other emerging preclinical, translational, and clinical data external to the trial.

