14.1.1 Schedule of Activities

Table 1 Schedule of Activities for Participants Enrolled on 2 Weeks On/1 Week Off Dosing (21-Day Cycles)

						Cyc	e 0														
	Pre- screening						Food Effect or ing Cohorts							Cycle 2			Additional Cycles		EOT/ ET°	Safety	Survival Follow- up ^e
		Screening ^a	Ef For	d (Fo fect) mula l (Pl ridgi	or ation K	Ef Forn	Fasted (Food Effect) or Formulation 2 (PK Bridging)					Cycle	1							Follow -up Visit ^d	
Trial Days	-180 to -1	-28 to -1	1ª	2	3 4	5 (+5)	6	7	8	1ª	1	8 (+2)	15 (+2)	1 (+3)	8 (+2)	15 (+2)	1 (+3) ^g	8 (+2) ^h	Within +7 days of Disc of	30 days after last	Every 90 days (±14 days)
Procedures/ Assessments ^f																			Trt date	dose (+14 days)	
Pre-screen informed consent	X																				
Screening/mai n informed consent		X																			
Inclusion/ exclusion criteria		X	X							X											

	Pre- screening	Screeninga				Cycl	e 0														
			PK	PK Cycle For Food Effe PK Bridging Cohor						PK Cycle ^b									EOT/	Safety Follow	Survival
			Ef For	d (Fo fect) mula 1 (PK ridgin	or tion	Fasted (Food Effect) or Formulation 2 (PK Bridging)				Fasted		Cycle	e 1	Cycle 2				tional cles	EO17	-up Visit ^d	Follow- up ^e
Trial Days	-180 to -1	-28 to -1	1ª	2	3 4	5 (+5)	6	7	8	1ª	1	8 (+2)	15 (+2)	1 (+3)	8 (+2)	15 (+2)	1 (+3) ^g	8 (+2) ^h	Within +7 days of Disc of Trt	30 days after last	Every 90 days (±14 days)
Procedures/ Assessments ^f																			date	dose (+14 days)	
Molecular eligibility ⁱ	X																				
Demographics	X																				
Medical/cance r history		X																			
Physical examination		X	X							X									X		
Abbreviated PE ^j														\mathbf{X}^{j}			\mathbf{X}^{j}			X	
Height ^k		X															X^k				
Weight		X	X							X				X			X		X	X	
Vital sign measurements ¹		X	X							X	X	X	X	X	X	X	X	X ^h	X	X	

							Cycle	e 0														
	-		PK	Cy PK	/cle K Br	For idgi	· Food I ing Coh	Effe	ct o	r	PK Cycle ^b							Additional		EOT/	Safety	Survival
	Pre- screening	Screening ^a	E1 For B1	1 (P ridg	t) or latio 'K jing)	Fasted (Food Effect) or Formulation 2 (PK Bridging)				Fasted		Cycle	:1	Cycle 2				tional cles	ET°	Follow -up Visit ^d	Follow- up ^e	
Trial Days	-180 to -1	-28 to -1	1ª	2	3	4	5 (+5)	6	7	8	1 ^a	1	8 (+2)	15 (+2)	1 (+3)	8 (+2)	15 (+2)	1 (+3) ^g	8 (+2) ^h	Within +7	30 days	Every 90 days
Procedures/ Assessments ^f																				days of Disc of Trt date	after last dose (+14 days)	(±14 days)
ECOG or Lansky performance status		X	X								X				X			X		X	X	

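### SAP 8.9.2 judges a schedule-based dose reduction by the length of the consecutive dosing run, so its own second example fails the rule, a switch with equal planned dosing counts as a reduction, and SAP 8.9 has no row for the result

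*SAP*

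**What the plan says.** SAP 8.9.2 gives two alternative criteria. The first is a lower total daily dose. The second covers days or weeks and carries one example for each. With its example for days, it reads "a decrease in the number of consecutive day (e.g., from 2 weeks on/1 week off to 3 days on/4 days off) or weeks". The example attached to weeks is "e.g. 2 weeks on/1 week off to 2 weeks on/2 weeks off". Neither criterion refers to planned dose per week or per cycle.

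The starting schedule is 2 weeks on/1 off. SAP 4.1 allows four more to be tried, in a sentence that begins "Additional treatment schedules, including daily dosing, 3 days on/4 days off, 1 week on/1 week off, or 2 weeks on/2 weeks off may also be". The schedules of activities in SAP 14.1.1 set cycle lengths of 21 or 28 days.

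The protocol synopsis says that "schedule changes, or intra-participant dose escalations, will be allowed for participants to manage AEs and/or maximize RP-1664 exposure and clinical benefit". It limits such changes to levels or frequencies that the Safety Review Committee has approved and that have cleared DLT evaluation.

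SAP 8.9 lists the exposure summaries. These include interruptions and "Any dose increases from the initial assigned dose", but no item for reductions.

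**The concern.** Schedules can shorten the dosing run, lengthen the rest period, or do both. A criterion that looks only at the run sees the first kind of change and not the second. That produces two errors at a constant daily dose: a real fall in planned dosing that the wording misses, and a neutral switch that it counts. Because the two criteria are joined by 'or', a change that lowers one component and raises the other is always a reduction, whatever the net effect.

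At stake is a descriptive count. One primary objective is to define a tolerated dose and schedule, and SAP 7 summarises data by dose level and dose schedule. A reduction count that depends on run length would not mean the same thing on each of the five schedules. Two programmers, one following the rule and one following the example, could also produce different tables.

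**Working it through.** The plan states no figure on this point, so there is nothing to reproduce first. The check applies the wording of 8.9.2 to the schedules in the documents.

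**Inputs.** Dosing days and cycle lengths come from SAP 14.1.1, for example "Schedule of Activities for Participants Enrolled on 2 Weeks On/1 Week Off Dosing (21-Day Cycles".

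**Step 1. Planned dosing days per week** = 7 × dosing days per cycle / cycle length in days.

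| Schedule | Longest run (days) | Dosing days / cycle days | Days per week |
|---|---|---|---|
| Daily | continuous | 21/21 | 7.00 |
| 2 on/1 off | 14 | 14/21 | 4.67 |
| 2 on/2 off | 14 | 14/28 | 3.50 |
| 1 on/1 off | 7 | 14/28 | 3.50 |
| 3 days on/4 off | 3 | 9/21 | 3.00 |

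**Step 2. The SAP's own examples, daily dose unchanged.**
- 2 on/1 off to 3 days on/4 off: the run falls from 14 to 3 days, so the rule is met. Planned dosing changes by 3.00/4.67 − 1 = −35.7%. Rule and example agree.
- 2 on/1 off to 2 on/2 off: the run is 14 days (two weeks) before and after, so neither criterion is met. Planned dosing changes by 3.50/4.67 − 1 = −25.0%. Rule and example disagree.

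**Step 3. All schedule-only switches.** Five schedules give 5 × 4 = 20 ordered switches. At a constant daily dose the wording agrees with planned dosing days per week on 18. The two disagreements are:
- 2 on/1 off to 2 on/2 off (−25.0%), missed by the wording;
- 2 on/2 off to 1 on/1 off (run 14 to 7 days; 14 dosing days per 28 in both, 0.0%), counted by the wording.

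No schedule-only switch both shortens the run and raises planned dosing.

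**Step 4. Dose and schedule changed together.** Let r be the new daily dose divided by the old. Net change in planned weekly dose = r × (new days per week / old days per week) − 1. The values of r are assumptions; the thresholds follow from Step 1.

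| Switch | Criterion met | Planned weekly dose rises when | Illustration |
|---|---|---|---|
| 2 on/1 off to 3 days on/4 off | shorter run | r > 4.67/3.00 = 1.556 | r = 1.75: +12.5%; r = 2.0: +28.6% |
| 3 days on/4 off to 2 on/1 off | lower daily dose | 3.00/4.67 = 0.643 < r < 1 | r = 0.80: +24.4% |
| 2 on/1 off to daily | lower daily dose | 4.67/7.00 = 0.667 < r < 1 | r = 0.75: +12.5% |

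Each is a reduction under 8.9.2. In the first row the daily dose also rises, so a participant still on the initially assigned dose before the switch would fall under the increases item in 8.9 as well.

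**The case against.** Several points on the other side have weight.

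- The second example is part of 8.9.2, and a programmer would probably code that switch as a reduction because it is named there. The intended result is clear. This stands as a reason to call it a drafting conflict. It does not settle which reading applies to switches that are not named.
- Without that example, only one schedule-only switch in 20 is misclassified, and both schedules in it are optional. This is correct.
- The combined cases need assumed dose ratios, and changes are limited to approved, cleared levels. Nothing shows that a qualifying pair will arise. This is also correct; the protocol synopsis does not rule such changes out, and no more can be said.
- Fewer consecutive days can reasonably be seen as de-intensification, since the rest week is there for marrow recovery. Likewise, calling a cut in daily dose an increase because weekly dose rises would be open to dispute. For this reason the daily-dose criterion should stay, and mixed changes should be shown apart, not relabelled.
- Actual and relative dose intensity already measure exposure. They are per-cycle quantities, however, and planned dose intensity is initial dose times planned dosing days per cycle. Three of the schedules plan 14 days per cycle over 21 or 28 days, so a per-cycle planned figure cannot separate 2 on/1 off from 2 on/2 off.

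A reader might infer that the reduction rate is a main input to dose selection and that it is contaminated by upward switches. The documents do not support this. They do not call it a main input, and 8.9 tabulates no such rate. The reduction output listed in SAP 12.2 is limited to treatment-related TEAEs leading to reduction. It may be taken from the recorded action taken with study drug, in which case 8.9.2 would not drive it.

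**Conclusion.** The point holds as a defect in an analysis definition. The schedule criterion in 8.9.2 conflicts with its own second example (−25% planned dosing days per week, not met by the wording) and counts one neutral switch (0%) as a reduction. These two results need no assumed doses. The labelling of a higher planned weekly dose as a reduction is possible only when dose and schedule move together; the thresholds are firm but the frequency is unknown. The missing reduction item in 8.9 can be seen directly in the list.

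The effect is limited to descriptive reduction counts that support the tolerability and schedule assessment. The TEAE endpoint and the actual dose intensity formula do not change. The conclusion assumes that 'consecutive' means an unbroken run of dosing, which is its ordinary sense. The available protocol text is the synopsis, so any dose-modification definition in its body could not be compared.

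**What to change.** This changes an analysis definition only and proposes no dose or schedule.

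1. In SAP 8.9.2, keep the first criterion: a lower total daily dose.
2. Restate the second as a decrease in planned dosing days per week, 7 × dosing days per cycle / cycle length in days, against the previous regimen. Both existing examples then meet the rule.
3. Tabulate separately (a) schedule changes that leave planned weekly dose unchanged and (b) combined changes in which daily dose and dosing days per week move in opposite directions, with the net change in planned weekly dose shown for each.
4. Add an item for any dose reduction to the list in SAP 8.9.

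The cost is SAP wording and a short derivation from dosing data already collected. The downside is that a few switches now labelled reductions would move to a separate row.
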